#### *Safety endpoint*

The primary safety endpoint will be the occurrence of any of the following:

- Serious Adverse Events
- Grade 3-4 Liver Toxicity following NIH common toxicity criteria (CTC), defined as transaminase increases to  $>225$  for men or  $>175$  for women/transgender (grade 3), or  $> 900$  for men or  $>700$  for women/transgender (grade 4)

#### *Secondary endpoints*

Secondary objectives are assessed with the adverse treatment outcomes defined above.

### **5. Interim analysis**

An interim analysis will be performed after the first 500 enrolled patients have finished the week 1+2 follow up visit. This interim analysis will have no effect on the continuation or conduct of the trial. Therefore no adaptation of sample size, multiplicity, ... is required.

Following analyses will be performed.

#### *In the intervention group*

The decrease from enrollment until week 2 in Auramine and FDA will be described using median and interquartile range. The number (%) of referrals to rapid DST will be presented. Counts (%) of the rapid DST result will be presented.

#### *In the control group*

The number (%) of referrals to rapid DST (based on body temperature) will be presented. Counts (%) of the rapid DST result will be presented.

The percentage of resistance missed will be compared between groups using the Chi-square or Fisher's exact test.

All analyses will be stratified on new vs retreatment cases. Analysis in the intervention group will be additionally stratified on period (2014 vs 2015).

## **6. Analysis of main efficacy outcomes: adverse treatment outcome**

Counts and proportions (and 95% CI) of patients with any adverse treatment outcome, and by adverse treatment outcome category, will be presented. The confidence intervals for proportions will be estimated using Wilson's score method. Odds ratio's (ORs) of treatment effect on any adverse treatment outcome and 95% CIs for the OR will be estimated from a logistic regression model with effects for arm (intervention vs control), hospital, and stratum (new/re-treatment case). The p-value for the test of no difference among arms will be presented. If the number of events is low a logistic regression model with an effect for hospital may be used instead of the full model proposed.

### **6.1. Subgroup analyses**

If the number of events is sufficient, subgroup analyses will be performed on the primary endpoint to assess consistency of response across patient populations. The following subgroup analyses will be performed:

- New and retreatment TB cases

The interaction between treatment differences and subgroup will be tested in the logistic regression model described above.

### **6.2. Other aspects**

#### *a. Multiplicity*

As this is a pilot estimation study with a single primary efficacy and safety endpoint, no multiplicity adjustments are needed. An interim analysis will be performed, but this analysis will not influence the continuation of the study.

#### *b. Missing data*

In the intention-to-treat analysis, patients who are lost-to-follow-up before the 12 month post treatment follow-up will be counted as adverse treatment outcomes, unless they are known to have moved outside of the area.

Missing values will be imputed based on a logistic regression model with factors for hospital and treatment group. We will randomly impute 10 datasets, perform the analysis on each imputed data set, and obtain final effect estimates by combining results using Rubin's rules.

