4.4 Randomization

Two randomization lists will be prepared at ITM prior to study start: one for new cases, one for retreatment cases. To ensure (approximate) treatment balance within study sites, the randomization list will be blocked. Treatment allocation will be concealed until the completion of the screening procedures and the final recruitment of the patient using sealed envelopes labelled with the randomization number and containing the treatment group allocation.

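### The imputation model in SAP 6.2b leaves out the new/retreatment stratum, so imputed outcomes dilute the stratum-specific results and any arm-by-stratum interaction

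*SAP*

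**What the plan says.** Missing data (SAP 6.2b): "Missing values will be imputed based on a logistic regression model with factors for hospital and treatment group". The section continues: "We will randomly impute 10 datasets, perform the analysis on each imputed data set", with results combined by Rubin's rules. The new/retreatment stratum is not named, and no other section adds it.

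The stratum appears in four other places:

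- Randomisation (Protocol 4.4): "Two randomization lists will be prepared at ITM prior to study start: one for new cases, one for retreatment cases".
- Primary model (SAP 6): "effects for arm (intervention vs control), hospital, and stratum (new/re-treatment case". If events are few, "a logistic regression model with an effect for hospital may be used instead of the full model proposed".
- Subgroup analysis (SAP 6.1): new versus retreatment is the only subgroup listed, and "The interaction between treatment differences and subgroup will be tested in the logistic regression model described above". This applies only if there are enough events.
- Description (Protocol 8.3.5): results are to be described separately for new and retreatment cases. This carries no condition.

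Three rules limit what is imputed. Patients lost before the 12-month post-treatment visit "will be counted as adverse treatment outcomes, unless they are known to have moved outside of the area" (SAP 6.2b). SAP 4.1.1 applies the same rule to patients who give no sputum. SAP 4.2 excludes patients who are transferred out, and those switched to the MDR regimen before another outcome applies.

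**The concern.** An imputation model should carry at least the terms of the analyses it feeds. Here it carries fewer. Within a hospital and arm, a new case and a retreatment case with missing outcomes are drawn from the same probability. Imputed records then hold no information on the stratum, and mixing them with observed records pulls the two strata towards each other.

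The stratum is not a neutral covariate in this trial. The control regimen differs by stratum (6 months for new cases, and 8 months with streptomycin for retreatment cases), while the intervention regimen is the same for both. The treatment contrast therefore differs by design, and an arm-by-stratum difference is plausible. Retreatment cases are probably a small minority, so the pooled rate lies close to the new-case rate and most of the distortion falls on the retreatment stratum.

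At stake are the retreatment-specific rates, the stratum coefficient and the interaction test.

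**Working it through.** **The plan's own figures.** The plan gives no figure for this point. The nearest are the planning rates in Protocol 8.4: 10% adverse outcome on control and 7% on intervention, with 1421 per arm for 80% power. A two-proportion calculation with continuity correction gives 1422, so the rates are usable as pooled inputs. The sample size is not affected.

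**Who is imputed.** Lost patients and patients without sputum count as adverse outcomes unless known to have moved. Transfers out are excluded. Protocol 3.1 defines a transfer out by an unknown treatment outcome, so a patient who finishes treatment and then moves away before the 12-month visit does not fit that definition. Such movers are the main group left for imputation. The SAP does not say so explicitly; this is an inference from the rules.

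**Formula.** With a fraction m of a stratum's outcomes imputed from a model without the stratum, the expected completed rate is

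(1 − m) × p_stratum + m × p_pooled.

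**Assumptions, not in the documents.** Retreatment share 10%; control risk 8.89% in new and 20% in retreatment cases. Pooled: 0.9 × 8.89% + 0.1 × 20% = 10.0%, matching Protocol 8.4.

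**Control retreatment rate, true value 20%:**

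- m = 2%: 0.98 × 20% + 0.02 × 10% = 19.8%
- m = 5%: 0.95 × 20% + 0.05 × 10% = 19.5%
- m = 10%: 0.90 × 20% + 0.10 × 10% = 19.0%

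The new-case rate moves much less. At m = 10% it is 0.90 × 8.89% + 0.10 × 10% = 9.0%.

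**Interaction.** Assume intervention risks of 5.56% (new) and 20% (retreatment), which pool to 0.9 × 5.56% + 0.1 × 20% = 7.0%. The true odds ratios are 0.603 in new and 1.00 in retreatment cases, a ratio of 1.66. At m = 10% the intervention rates become 0.90 × 5.56% + 0.10 × 7% = 5.7% and 0.90 × 20% + 0.10 × 7% = 18.7%. The odds ratios are then 0.612 and 0.981, and their ratio is 1.60. On the log scale this is 0.472 against 0.505, a shrinkage of about 7%. At m = 5% the ratio is 1.63; at m = 2% it is 1.65. With 10% of new-case and 20% of retreatment outcomes missing it is 1.57.

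**Overall arm rates.** With equal missingness they stay at 10.0% and 7.0%. In the unequal case just given they are 9.9% and 6.9%.

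**Simulation.** 1000 patients, the risks above, three hospital levels, 10% missing, 10 imputations and 150 runs per setting. The two settings were simulated separately, so their full-data values differ.

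- Stratum omitted: stratum log odds ratio 1.07 against 1.17 in the full data; arm log odds ratio −0.367 against −0.370.
- Stratum and arm-by-stratum included: stratum log odds ratio 1.17 against 1.18.

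**The case against.** Most of the case against concerns size, and much of it stands.

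- **Little is imputed.** The rules above leave mainly known movers. The documents give no number of them, so the fractions used here are assumptions.
- **The 20% retreatment risk is assumed.** The MDR-TB estimates in Protocol 1.1 (1.4% in new, 29% in retreatment cases) support a prognostic gap only indirectly. Patients found resistant before treatment are not eligible, and those switched to the MDR regimen later are excluded from the outcome analysis.
- **The interaction test is conditional and weak.** The only retreatment share in the documents is national: 7366 of about 100,000 smear-positives, or about 7%. In 1000 patients that is about 70, with 7 to 14 events at a risk of 10 to 20%. If 10% of those 70 were imputed, a 10-point error in risk would misplace 7 × 0.10 = 0.7 of an event. The primary model may also drop the stratum. The separate descriptions in Protocol 8.3.5 would still be affected.

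Two stronger readings are tempting and are not supported.

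- **That Rubin's rules give wrong standard errors here.** A further simulation used 7% retreatment share, control risks of 9.25% (new) and 20% (retreatment), 10 imputations and 600 runs. Coverage of the 95% interval for the arm effect was 94.8%, 95.0% and 94.3% at 2%, 5% and 10% missing. For the stratum effect it was 97 to 98%, slightly conservative. A repeat with three and with eight hospital levels gave the same broad picture. These checks cover main effects only, but they show no practical loss.
- **That the imputation model should also carry the last on-treatment smear.** Under SAP 4.2 a positive sputum at 5 months or later is itself failure. Such a covariate would predict the outcome perfectly in those patients and cause separation. Patients still to be imputed after treatment would nearly all be smear-negative, so it would add little.

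**Conclusion.** The omission is real, and its direction is clear: imputed outcomes follow the rate pooled over strata within hospital and arm. The stratum effect, the contrast between stratum-specific rates and any true interaction are diluted roughly in proportion to the imputed fraction. Under the assumed risks, a 20% retreatment rate is reported as 19.5% at 5% imputed and 19% at 10%, and the interaction loses about 7% on the log scale at 10%.

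A reader might infer that the primary comparison between arms is biased. The calculations do not support that: the overall arm effect barely moves, even with missingness twice as high in the retreatment stratum.

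The sizes rest on assumed stratum risks, retreatment share and imputed fractions. If the strata have similar risks, or almost nothing is imputed, the effect vanishes. It is a minor point, worth correcting because the correction is so simple.

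**What to change.** In SAP 6.2b, let the imputation model read: *factors for hospital, treatment group and stratum (new/retreatment)*. Add treatment-by-stratum when the interaction test in SAP 6.1 is run and event numbers allow. State that the stratum main effect alone is the fallback.

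State in the same section which patients are imputed, as distinct from those counted as adverse outcomes or excluded as transfers out.

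The cost is a line or two in the SAP. No new data are needed, and the sample size does not change. The one downside is sparse cells: at a 7% retreatment share there are about 35 retreatment patients per arm, with about 2 to 4 events at a risk of 7 to 10%. That is thin support for an interaction term alongside the hospital factors, which is why the main effect should be the default.

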8.1 Study hypotheses

This study is a pilot study to estimate the differences in the incidences in adverse treatment outcomes and excess toxicity. Consequently, the focus will be in describing event rates in each study arm and estimating the differences in event rates using odds-ratio's together with 95% confidence intervals (CIs) and not on formal hypothesis testing. P-values for comparisons of event rates (adverse treatment outcomes and safety endpoints) between intervention and control arms will be provided, but will need to be interpreted with care.

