8.4 Sample size and power

The sample size of two times 500 patients is a trade-off between precision and exposing an excessively high number of patients to potentially more toxic treatment. Power has not been taken into account, but if the results are favourable large scale cluster-randomized study will be designed to bring definitive proof.

The registered incidence of clinically apparent hepatitis from any cause during TB treatment is 1.5% for the study population. With the proposed sample size, an increase by at least 2% compared to the control arm will attain statistical significance ($p=0.047$).

With the standard (=control) regimens and definitions, about 2% failures and 2% relapses are currently notified by the DF project, but only 50% of those are culture-positive, and about half of the culture positive failures and relapses are rifampicin-resistant. Overall cure rate (new and retreatment cases together) is close to 90%, with 4% default and 4% deaths. Based on the data from 2010 about 20 cases with rifampicin resistance may be enrolled, 10 in each arm. We estimate that the more effective study regimen plus early detection of serious drug resistance rolled over to MDR-TB

treatment will prevent drug resistant failure and relapse, reduce rifampicin susceptible relapse to an estimated two third, and reduce death and default because of unrecognized rifampicin resistance to 80% of the control arm. This total estimated reduction of unfavourable outcome from 10% to 7% remains non-significant with the targeted enrolment of two times 500 cases. With 80% power and 95% confidence level, 2 x 1421 patients would have to be enrolled, which is not feasible and also difficult to justify. However, a slightly larger reduction of unfavourable outcome from 10% to 6.5% comparing two arms of 500 cases each would already result in a significant p-value. Additional evidence will be obtained studying *rpoB* mutations, initially (all smear-positives) and at time of failure or relapse (only in the few such cases expected). Absence of low-level resistance mutations only among patients with unfavourable outcome on the high-dose arm, while they were present among new cases in both arms, will be interpreted as additional evidence of effectiveness of the increased dosing.

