#### 4.2. Efficacy study endpoints

##### *Primary endpoint*

The primary efficacy endpoint is the incidence of adverse treatment outcomes. Following the WHO guidelines from 2010, as currently in use in the NTP in Bangladesh, an adverse treatment outcome is defined as any occurrence of the following:

- Relapse: Cured previously from TB or completed treatment for TB and now having bacteriologically positive sputum for TB (at 12 months follow-up or at an earlier time point)
- Default: The patient whose treatment was interrupted for 2 consecutive months or more.

- Failure: Sputum positive for TB at 5 months or later during treatment. Failure will also be declared if the regimen has to be changed for at least 2 drugs due to adverse events.
- Death: All-cause mortality between case registration and end of TB treatment (related or not to TB or TB treatment)

Patients who are transferred out will be excluded from the outcome analysis.

In line with current WHO recommendations, patients detected with MDR-TB or rifampicin resistance before any outcome applies and switched to the MDR-TB regimen will be excluded from the outcome analysis.

Analyses will be performed using the NTP smear-based recurrence (failure, relapse) definitions, but as a secondary approach culture-based definitions will be used. In each analysis, if a patient has two events for the analysis of interest, the first endpoint will be taken into account, except for cured/completed followed by relapse which is considered as relapse.

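### If SAP 6.2b imputes the composite for cured patients who moved away, it gives them the risk of every adverse outcome when only relapse is still possible; this modestly inflates each arm's incidence

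*SAP*

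**What the plan says.** SAP 6.2b has two rules for the intention-to-treat analysis. Patients lost before the 12-month post-treatment visit "will be counted as adverse treatment outcomes, unless they are known to have moved outside of the area". The next paragraph says "Missing values will be imputed based on a logistic regression model with factors for hospital and treatment group", and continues: "We will randomly impute 10 datasets, perform the analysis on each imputed data set", with effect estimates pooled by Rubin's rules. It does not name the variable that is imputed or the patients concerned.

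SAP 4.2 adds: "Patients who are transferred out will be excluded from the outcome analysis". Protocol 3.1 limits that label to patients whose treatment outcome is not known, so a patient already declared cured who later moves is not a transfer-out.

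SAP 4.2 also fixes when each component can occur. Failure is "Sputum positive for TB at 5 months or later during treatment" (or a forced change of at least two drugs), default is an interruption of treatment, and death counts only up to the end of treatment. Relapse is the only component that can follow cure or completion.

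Protocol 8.1 sets the aim of the analysis: "Consequently, the focus will be in describing event rates in each study arm".

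**The concern.** Taken together, these rules leave one main group with a missing primary outcome: patients recorded as cured or completed who are known to have moved before the 12-month visit. They have already passed through treatment without death, default or failure. The stated model has site and arm but not the recorded end-of-treatment outcome. If it imputes the composite, it draws their result at the arm's overall adverse risk. That risk is fitted on data that include on-treatment deaths, defaults and failures, plus the lost patients set to adverse by rule. Adding the new/retreatment stratum to the model would not correct this.

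At stake is the incidence in each arm, which the protocol makes the focus. SAP section 6 also reports proportions by outcome category. An imputed composite event has no category, and in a cured patient it could only be a relapse.

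**Working it through.** **Inputs.** Protocol 8.4: "about 2% failures and 2% relapses are currently notified by the DF project", with 4% default and 4% deaths; planning rates 10% (control) and 7% (intervention); rifampicin-susceptible relapse reduced to two thirds. Protocol 4.3: 500 per arm. The four control components add to 2 + 2 + 4 + 4 = 12%, not the 10% used for planning, so both are shown.

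**Assumptions.** The documents do not give the share of cured patients who move (*m*) or the share of the remaining cured patients who are lost and set to adverse (*L*). I take *m* = 2%, 5%, 10% and *L* = 0%, 5%, 10%. Intervention relapse is taken as two thirds of 2%, or 1.33%. Movers are assumed to relapse like other cured patients.

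**The plan's own figure.** The SAP gives no number for the imputation. The nearest stated figure, 1421 per arm for 10% v 7%, is reproduced: the two-proportion formula with continuity correction gives 1422 (without correction, 1356). The planning rates are therefore read correctly.

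**Formulas.** Let *e* be the on-treatment adverse share, *r* the relapse share and *c* = 1 − *e* the cured or completed share.

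- Imputed risk = [*e* + (1 − *m*)*r*] / (1 − *mc*)
- Relapse risk given cure = *r*/*c*
- Excess events per 500 = 500 × *mc* × (imputed risk − *r*/*c*)

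**Example: control, 10% composite, *m* = 5%.** *e* = 8%, *r* = 2%, *c* = 92%.

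- Imputed risk = (0.08 + 0.019)/(1 − 0.046) = 10.38%
- Relapse risk = 0.02/0.92 = 2.17%
- Movers = 23 per arm; expected imputed events 2.39 v 0.50; excess 1.89, or 0.38 points

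With the 12% component sum, relapse given cure is 0.02/0.90 = 2.22%. In the intervention arm (7%, relapse 1.33%) it is 1.33/94.33 = 1.41%.

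| Cured who move | Control, 10%: imputed risk; excess | Control, 12%: imputed risk; excess | Intervention, 7%: imputed risk; excess |
|---|---|---|---|
| 2% | 10.15%; 0.73 events (0.15 points) | 12.18%; 0.90 (0.18) | 7.11%; 0.54 (0.11) |
| 5% | 10.38%; 1.89 (0.38) | 12.46%; 2.30 (0.46) | 7.28%; 1.38 (0.28) |
| 10% | 10.79%; 3.96 (0.79) | 12.97%; 4.84 (0.97) | 7.58%; 2.91 (0.58) |

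**Losses set to adverse.** The numerator becomes *e* + (1 − *m*)[*Lc* + (1 − *L*)*r*]. With *L* = 5% and *m* = 5% on the 10% rate, the imputed control risk is (0.08 + 0.06175)/0.954 = 14.86%, and the excess due to movers is 2.92 events. With *L* = 10% and *m* = 10%, these are 19.71% and 8.07 events.

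**Between arms (*L* = 0).** On 10% v 7%, the risk difference goes from 3.00 to 10.38 − 7.28 = 3.10 points at 5% movers and to 10.79 − 7.58 = 3.21 at 10%, an overstatement of about 3% and 7%. A simulation (1,500 trials, 10 imputations each, hospital effect left out) gives an odds ratio of 0.679 on full data and 0.679 after composite imputation at 5% movers, and 0.673 v 0.674 at 10%.

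**Dropping movers.** Imputing at the observed-patient risk makes the arm incidence equal to that risk. Leaving movers out therefore gives the same inflated proportion.

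**With relapse-only imputation.** In the same simulation at 5% movers, incidence is 10.00% and 7.05%, against 10.38% and 7.32% with composite imputation and 9.99% and 7.04% on full data.

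**The case against.** The strongest reply is that the SAP never says cured movers are imputed, or that the composite is the variable imputed. It only exempts movers from the loss rule; they could keep their end-of-treatment result. That stands: the point rests on reading three rules together and must be stated conditionally.

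Nor are cured movers the only candidates. Protocol 4.5 lists withdrawal of consent and withdrawal by the investigator apart from loss to follow-up. A patient withdrawn during treatment may have several components still open, and composite imputation is then not clearly wrong. That also stands, and the fix must leave those patients a rule.

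Rubin pooling is promised only for effect estimates, which in SAP section 6 means the odds ratio. The SAP does not say that the Wilson proportions use imputed data. This limits the claim but does not rescue the proportions, since dropping movers inflates them equally.

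A reader might infer that the treatment comparison is materially biased, for instance by setting the 0.46-point control shift against the planned 3-point effect. The documents' figures do not support that. A one-arm shift is not comparable with a between-arm difference; both arms shift the same way. One arm's 95% half-width at 12% is 1.96 × √(0.12 × 0.88/500) = 2.8 points, so the shift is also small beside sampling error.

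Finally, the loss rule itself can matter more. At 5% movers on the 10% rate, setting 5% or 10% of the remaining cured patients to adverse takes control incidence from 10.00% to 14.28% or 18.55%, about 21 or 43 events per 500. The fix below does not address that rule.

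**Conclusion.** The point holds in conditional form. If SAP 6.2b imputes the composite as written, cured or completed movers receive about 5 to 6 times their relapse risk in controls at 5% movers (10.38/2.17 = 4.8; 12.46/2.22 = 5.6), before any losses are set to adverse. Control incidence is inflated by about 0.15-0.2, 0.4-0.5 and 0.8-1.0 points at 2%, 5% and 10% movers, and by more if many others are lost and set to adverse. The risk difference is overstated by about 3-7% at 5-10% movers, and the odds ratio is essentially unchanged if moving is similar in both arms.

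The size depends on a mover share the documents do not give, and on movers relapsing like other cured patients. This is a minor, inexpensive improvement to the reported rates. It is not a threat to the treatment comparison.

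**What to change.** In SAP 6.2b:

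1. State which patients have their outcome imputed, and that the reported proportions as well as the odds ratio use the imputed data.
2. For patients recorded as cured or completed who moved before the 12-month visit (V9), impute relapse only. Fit the model to cured or completed patients with observed relapse status, leaving out those set to adverse by rule. Include arm, and site if events allow; keep the model simple or penalise it. Then derive the composite from the recorded end-of-treatment outcome and the imputed relapse status.
3. Keep composite imputation for patients whose end-of-treatment outcome is itself missing, such as withdrawals during treatment.

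The cost is a few lines of SAP text and code. No new data are needed, because the end-of-treatment outcome is already recorded. The downside is that the relapse model rests on about 10 events per arm (2% of 500 in controls, fewer if the intervention works) and on the assumption that movers relapse like other cured patients.
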